4.2. Treatment Groups

The trial is randomised with two arms and with equal allocation of participants in a 1:1 ratio to these arms. **Active Arm**: IPE for 12 months; **Placebo Arm**: Inulin for 12 months.

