4.5. Sample Size

On the basis outlined below, a sample size of 270 randomised participants (135 per arm) was chosen to provide 90% power to detect a 2kg difference between arms in mean body weight change over 12 months using a two-sided 5% significance test, assuming a 4.35kg SD and with 25% dropout allowance.

Determination of the primary outcome effect size:

In the randomised proof of concept trial, the difference between arms in the change in body weight over 24 weeks was 1.4kg (95% CI: -0.3 to 3.1), p=0.099. Using a Bayesian method recommended for preliminary trials in which evidence in the 95% CI is translated into probabilities, there was a 95% posterior probability of an underlying positive between-arm difference favouring the intervention (11). The posterior probability of intervention-favouring differences greater than 1kg, than 1.5kg, and 2kg were respectively 69%, 47% and 25% based on 24-week intervention. The difference increased in magnitude through successive 8-week, 16-week, and 24-week timepoints. By 24 weeks there were significant reductions in the proportion of intervention participants gaining \geq 3%, and \geq 5% of body weight from a mean baseline of 90kg. We therefore chose a 2kg between-arm 12-month effect size.

Determination of the primary outcome variability:

The chosen detectable effect size of 2kg agreed with that in a weight gain prevention trial conducted over 9 months in young adults (12) by also aiming to detect a 2kg effect, and achieved 4.3kg with 81% retention. The pooled standard deviation (SD) for body weight change was 4.35kg.

Power to detect the effect:

We set a 90% power to detect the primary outcome effect size of 2kg.

Determination of the sample size based on the primary outcome:

The sample size was set to be **270 participants, 135 per arm**. This involves a 25% allowance loss of 12-month primary outcomes, and two-sided statistical testing at the 5% significance level, implying that 202 subjects are required to be followed up with a valid primary outcome. Further adjustment for baseline body weight is expected to improve the precision of the estimated treatment effect.

Power calculation for Mechanistic outcomes:

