7.5. Safety Analysis

Adverse events and SAEs will be reported in terms of the number of participants with at least one event per arm and using descriptive statistics, as unadjusted patient proportions within and between arms with 95% confidence intervals using exact methods where appropriate, such as the Wilson method (26) (with none versus with at least one event). Numerators and denominators will be presented. For the most prominent gastrointestinal disorders (in at least 10% of participants in either treatment group), as well as AEs that lead to treatment discontinuation, details of the overall number of events, timing to reporting of first such event by participant (median (IQR) time since randomisation), severity, and duration will be described as per preferred term. Denominators will generally be participants over the trial period, although between-visit stratification will be considered, as will a person-years denominator depending on the variability in follow-up. *P*-values will not be used taking account of guidance given in the CONSORT statement extension for harms (27, 28). Volcano (space-saving graphical summary) or dot plots may also be presented if frequent adverse events occur(29).

Objective	Variable	Main summary statistic	Statistical method for comparison between arms and inference type
7 To determine compliance during the 12-month intervention	Firstly, by accountability of returned used sachets. Secondly, communicated verbally by the participant (such during COVID periods where visits were done remotely)	Proportions of 50% to 95% compliance (in steps of 5%)	Difference in proportions with 95% CIs Comparison of compliance distributions
	Percentage compliance for a subject will then be defined as number of used sachets divided by the total number of sachets expected to have been taken over the 12-month study period)*100%.† In periods where the sachets have not been returned it will be assumed that the compliance was the same as in the average of the other periods (0- 2months, 2 -6 months, 6 -12months). For participants reporting treatment discontinuation or that were lost to follow-up, we will consider zero used sachets from these timepoints onwards. Those with no treatment compliance data will be regarded as below 50% compliance for purpose of analysis.	Medians (IQR)	Difference in medians

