7.6. Compliance Analysis

[†]If return of sachets is low (median of used and unused <50% of those dispensed) we will check for the correlation between this objective measurement of compliance (accountability of unused sachets) and the self-reported measurement 'How many times did subject miss a sachet since the previous study visit?' and if it turns to be high (\geq 0.7), and this self-reported measurement has less missing data, than the self-reported measure will be used to assess compliance. For subjects who become pregnant, only the time up to this event will count when assessing compliance.

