7.7. Supplementary analysis: The effect of IPE in a more compliant population

Attributes of the supplementary and	Attributes of the supplementary analysis estimand:				
1 Population of interest: Defined by those participants eligible to be in the trial *					
2 Variable (endpoint) of interest: A	Already described in section				
3 Treatment of interest:	Already described in section 2.3				
4 Intercurrent events*:		Strategy to deal with the			
		intercurrent event:			
a) Death		Treatment policy			
b) Pregnancy/ Treatment discor	ntinuation due to pregnancy	Hypothetical strategy			
c) Concomitant 'treatment': Eg	. weight loss program /bariatric surgery/	Hypothetical strategy			
gym personal trainer					
d) AE/Development of an illnes	ss, say cancer or COVID-19 or other	Hypothetical strategy			
disease that affects participar	nts' weight				
e) Treatment discontinuation du	ue to an AE not affecting participants	Treatment policy			
weight					
f) Treatment discontinuation du	ue to lack of efficacy (increase in weight	Treatment policy			
g) Treatment discontinuation du	ue to run out of supply	Treatment policy			
h) Treatment discontinuation du	ue to being indirectly affected by	Treatment policy			
COVID-19 (preventing from	coming to clinical visits)				
5 Population-level summary for the variable: Difference in weight gain between those taking IPE and control inulin					
after 12 months					

*Just to emphasise this population is different from that addressed in section 7.2.2

In this analysis, the strategies to address the intercurrent events are the same as the ones described in section 7.2.2, except for AE or concomitant 'treatments' affecting a participant's weight, for which the hypothetical scenario is envisage. Thus, as before, measurements occurring after these events will be removed from the analysis and the LME model will be refitted.

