Inulin Control	$= N_{c} - (N_{12}/N_{1})*N_{c}$	$= (N_{12}/N_1)^*N_C$	Nc
	$= (M_{C} - (N_{12}/N_{1})*M_{12})/(N_{11}/N_{1})$	= M ₁₂	Mc

(Statistics preceded by an "=" are unobserved, and are estimated from the observed statistics.) The method is adapted to a more plausible MAR assumption by replacing the sample sizes at follow-up by those at baseline. In the presence of missing compliance, it will be primarily assumed that the participant is a non-complier.

The CACE estimate will instead be obtained from the analysis LME model applying the strategies in table 7.7, as this adjusts for baseline and refers to the population for the supplementary investigation. The CACE estimate is the ratio of the estimated treatment effect to the proportion compliant, following the rule of thumb (31) (estimate LME/ proportion compliant).

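### Compliance stops being counted at pregnancy but not at the other two events that table 7.7 treats hypothetically, which moves the exploratory CACE estimate away from zero

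*SAP*

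**What the plan says.** Four rules in the SAP meet here.

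- **Compliance definition (table of section 7.6).** Percentage compliance is the "number of used sachets divided by the total number of sachets expected to have been taken over the 12-month study period". Anyone who reports stopping treatment, or is lost to follow-up, is given zero used sachets from that time, whatever the reason.
- **The one exception (footnote to section 7.6).** "For subjects who become pregnant, only the time up to this event will count when assessing compliance". No other event is exempted.
- **Event handling for the supplementary estimand (section 7.7).** The table gives a hypothetical strategy to three events: (b) pregnancy, (c) concomitant treatment such as a weight-loss programme, bariatric surgery or a trainer, and (d) an AE or illness that affects weight. For (c) and (d), as for pregnancy, "measurements occurring after these events will be removed from the analysis and the LME model will be refitted".
- **The estimator (section 7.7.1).** "The CACE estimate is the ratio of the estimated treatment effect to the proportion compliant". The treatment effect comes from the mixed model under the section 7.7 strategies, and the thresholds run from 50% to 95%.

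Section 6.7 says that the compliance variable also serves the supplementary investigation. Nothing in the SAP gives the CACE a compliance definition of its own.

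**The concern.** The numerator and the denominator of the CACE should describe the same setting. For pregnancy they do: later weights are dropped and later sachets are not expected. For events (c) and (d), only the weights are dropped. Someone who takes every sachet until a weight-affecting illness and then stops because of it is event-free above the line. Below it, the same person may be a non-complier on account of the event.

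This conflicts with an assumption the SAP itself makes. The exclusion restriction in section 7.7.1 requires non-compliers to have the same mean outcome in both arms. Under missing at random, the mixed model in effect fills in the removed weights of an IPE participant from other IPE participants, with the arm effect included. A person classed as a non-complier then carries a treatment effect, purely because of how the event was handled.

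At stake is an overstated complier effect, in an analysis that section 7.7.1 presents as a better estimate of the true effect. Because the size can vary with the threshold, part of any gradient between 50% and 95% could be mistaken for a dose-response.

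**Working it through.** **The plan's own figure.** The SAP gives no value for the CACE or for the proportion compliant. The only figure that can be checked is the sample size in section 4.5, which states that "202 subjects are required to be followed up with a valid primary outcome". Its inputs are a 2 kg effect, an SD of 4.35 kg, 90% power, a two-sided 5% level and 25% loss. A two-sided t-test with 101 per arm has 90.2% power, so 202 in total, and 202/0.75 = 269.3, rounded up to 270. The figure reproduces. It is used below only to set a scale for the standard error.

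**Step 1: one participant.** A fully adherent participant who stops at month t scores 100 × t/12 under the section 7.6 table.

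| Stop at month | Score, (c) or (d) | Score under the pregnancy rule |
|---|---|---|
| 2 | 16.7% | 100% |
| 4 | 33.3% | 100% |
| 6 | 50.0% | 100% |
| 8 | 66.7% | 100% |
| 10 | 83.3% | 100% |

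**Step 2: when the stop matters.** The participant falls below the threshold if the stop comes before month 12 × threshold / adherence. For full adherence this is month 6.0 at the 50% threshold, 9.0 at 75% and 11.4 at 95%. At 80% adherence and the 50% threshold it is 12 × 0.50/0.80 = 7.5. The window therefore tends to widen as the threshold rises.

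**Step 3: the ratio.** Let p be the proportion of the IPE arm who would comply if event-free. Let e be the share of would-be compliers who fall below the threshold because they stopped after event (c) or (d). Neither is in the SAP, so both are assumed. Such events are taken to be equally likely in would-be compliers and others.

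- Proportion compliant as the SAP counts it: p(1-e)
- CACE under the SAP: effect / [p(1-e)]
- CACE with a matched denominator: effect / p
- Ratio of the two: 1/(1-e), whatever p is

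| e | 1/(1-e) | CACE under the SAP, effect 2 kg, p = 0.70 | Matched CACE |
|---|---|---|---|
| 2% | 1.020 | 2/0.686 = 2.92 kg | 2.86 kg |
| 5% | 1.053 | 2/0.665 = 3.01 kg | 2.86 kg |
| 10% | 1.111 | 2/0.630 = 3.17 kg | 2.86 kg |

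A second example starts from 60% compliant as counted by the SAP, with e = 5%. The SAP gives 2.0/0.60 = 3.33 kg. The matched proportion is 0.60/0.95 = 0.632, which gives 2.0/0.632 = 3.17 kg.

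**Step 4: check by simulation.** There were 400,000 simulated participants for each e, with p = 0.70 and a true CACE of -2.50 kg. The 12-month weights of those with an event were removed, and a baseline-adjusted ANCOVA stood in for the mixed model. For e of 2%, 5% and 10% the SAP rule gave -2.56, -2.61 and -2.78 kg. The matched rule gave -2.51, -2.48 and -2.50 kg.

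**Step 5: scale.** The unadjusted standard error of the treatment effect is 4.35 × √(2/101) = 0.61 kg. Divided by 0.60 it is 1.02 kg for the CACE. The shift in the second example, 3.333 - 3.167 = 0.167 kg, is about 0.16 of that standard error.

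**The case against.** The case for leaving the plan alone has several parts.

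- **Stopping is real non-compliance.** For descriptive reporting that is right. For the CACE, the SAP has already set the argument aside for pregnancy, and section 7.7 puts (c) and (d) under the same strategy.
- **The difference may be deliberate.** Row (b) of the table names discontinuation due to pregnancy, whereas rows (c) and (d) name no discontinuation. The authors may regard sachets as still expected after (c) and (d). The SAP does not say so, so this remains one possible reading.
- **The events should be uncommon.** Participants are aged 20-40, not obese, and free of diagnosed cancer, diabetes and heart disease. A trainer, a diet programme or COVID-19 need not stop anyone taking sachets. Section 7.11 does not expect relevant deviations in many patients. This stands, and it makes the upper end of the assumed range unlikely.
- **Little hangs on it.** The analysis is supplementary and exploratory. If the proportion is treated as fixed, the estimate and its interval scale together, so significance does not change. This also stands.

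A reader might infer three stronger things that the SAP does not support.

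1. *That the CACE must be inflated at every threshold.* A fully adherent participant who stops at or after month 6 still scores at least 50% and stays a complier at that threshold.
2. *That the overstatement could reach 20%.* That comes from counting everyone affected as a complier. For example, 60% compliant plus 5% affected gives 2.0/0.65 = 3.08 kg. With 50% compliant and 10% affected, 0.60/0.50 = 1.20. The numerator does not match this. Apart from what earlier weights reveal, the model gives those removed the average outcome of their arm, so the matching denominator is 0.60/0.95 and not 0.65.
3. *That everyone with event (c) or (d) is misclassified.* Those who continue sachets keep their observed counts and are not affected.

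**Conclusion.** The mismatch is in the text: three events are handled alike in the numerator and only one is matched in the denominator, with no reason given. The effect is to move the CACE away from zero by about 1/(1-e). That is roughly 2%, 5% and 11% at e of 2%, 5% and 10%, or 3.33 kg against 3.17 kg in the worked example.

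The size rests on assumptions that the SAP cannot settle. They are the event rate, how often the event leads to stopping, how early the stop comes, and equal event rates in would-be compliers and others. The bias is smallest at 50% and tends to grow towards 95%. A value of e near 10% is probably too high for this population.

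Only the exploratory CACE is affected. The primary analysis uses treatment policy for (c) and (d) and makes no use of compliance. This is a minor point, worth correcting because the correction is cheap.

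**What to change.** Add one rule to section 7.7.1, for the compliance used there only. For participants who discontinue sachets because of a concomitant weight treatment or a weight-affecting illness or AE, count sachets used and sachets expected only up to that event, as section 7.6 already does for pregnancy. Leave participants who continue sachets after such an event on their observed counts. Keep full 12-month compliance for the descriptive analysis in section 7.6. If the authors prefer to keep the present rule, they should state why pregnancy alone is exempt.

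No new data are needed. Event dates are already required to remove the weights, and section 7.1.6 already summarises withdrawals from intervention by reason and timing. The rule should not be applied to those who continue, because sachets are counted only at 2, 6 and 12 months, so use up to a mid-period date is not observed for them. If a stop comes some time after the event, the rule should say which date closes the count.

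The cost is that compliance is judged over a shorter period for these participants, which makes a high threshold easier to meet. The CACE becomes slightly smaller. If nearly all of them had complied before the event, the rule would over-correct a little: 3.08 kg against 3.17 kg in the example, about 3% too low, compared with about 5% too high now.

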7.7. Supplementary analysis: The effect of IPE in a more compliant population

Attributes of the supplementary and	Attributes of the supplementary analysis estimand:				
1 Population of interest: Defined by those participants eligible to be in the trial *					
2 Variable (endpoint) of interest: A	Already described in section				
3 Treatment of interest:	Already described in section 2.3				
4 Intercurrent events*:		Strategy to deal with the			
		intercurrent event:			
a) Death		Treatment policy			
b) Pregnancy/ Treatment discor	ntinuation due to pregnancy	Hypothetical strategy			
c) Concomitant 'treatment': Eg	. weight loss program /bariatric surgery/	Hypothetical strategy			
gym personal trainer					
d) AE/Development of an illnes	ss, say cancer or COVID-19 or other	Hypothetical strategy			
disease that affects participar	nts' weight				
e) Treatment discontinuation du	ue to an AE not affecting participants	Treatment policy			
weight					
f) Treatment discontinuation du	ue to lack of efficacy (increase in weight	Treatment policy			
g) Treatment discontinuation du	ue to run out of supply	Treatment policy			
h) Treatment discontinuation du	ue to being indirectly affected by	Treatment policy			
COVID-19 (preventing from	coming to clinical visits)				
5 Population-level summary for the variable: Difference in weight gain between those taking IPE and control inulin					
after 12 months					

*Just to emphasise this population is different from that addressed in section 7.2.2

In this analysis, the strategies to address the intercurrent events are the same as the ones described in section 7.2.2, except for AE or concomitant 'treatments' affecting a participant's weight, for which the hypothetical scenario is envisage. Thus, as before, measurements occurring after these events will be removed from the analysis and the LME model will be refitted.

7.7.1 Sensitivity analysis for non-compliance

White et al. also recommend that analyses allowing for non-response and low intervention uptake (or compliance) are specified in advance in the analysis plan (24). "Incomplete uptake of trial interventions often means that randomised groups have more similar experience than the investigators had intended, which usually causes the difference in outcomes to be smaller than it would have been with better uptake." (24). This means that low compliance with the IPE may bring about two groups that have more similar intervention experience to each other than was planned (i.e. intervention more similar to control through low compliance).

Further to the previous sensitivity analysis we will conduct an analysis estimating the effect of IPE versus Inulin control on the primary outcome in a more highly compliant population, whilst respecting randomisation. This approach should provide a better estimate of the true effect without suffering from potential biases seen in a per-protocol analysis.

Therefore a complier average causal effect (CACE) analysis will be carried out as recommended and outlined by Dunn et al. (30). The Complier-Average Causal Effect (CACE) estimate is the comparison of the average outcome of the compliers in the IPE arm with the average outcome of the comparable group ("would-be compliers") in the Inulin Control arm. Since it is not well studied as to the number of sachets needed to be taken over a 12 month period for the IPE to have an effect, if there is one, alternative levels of compliance will considered, ranging from 50% to 95%, and is therefore more exploratory than the planned primary analysis. The outline of the approach to be taken is given here:

Sample sizes (N) and means (M) are deduced for the Inulin control "would-be compliers" and "would-benoncompliers" in the following table by assuming that the proportion of intervention group compliers, and control group would-be compliers, is the same under randomisation, and that would-be non-compliers in the control group would have the same mean outcome as non-compliers in the intervention group (the exclusion

restriction as	sumption). The sample sizes refer to th	ose followed-up with primary outc	ome data (bod	ly weight
at 12 months).				
Arm	Compliers	Noncompliers	All	
	(≥ chosen threshold %)	(< chosen threshold %)		

/ 1111	complicits	Noncomplicity	7.01
	(≥ chosen threshold %)	(< chosen threshold %)	
IPE	N _{I1}	N ₁₂	N
	Mil	M _{I2}	M
Inulin Control	$= N_{c} - (N_{12}/N_{1})*N_{c}$	$= (N_{12}/N_1)^*N_C$	Nc
	$= (M_{C} - (N_{12}/N_{1})*M_{12})/(N_{11}/N_{1})$	= M ₁₂	Mc

(Statistics preceded by an "=" are unobserved, and are estimated from the observed statistics.) The method is adapted to a more plausible MAR assumption by replacing the sample sizes at follow-up by those at baseline. In the presence of missing compliance, it will be primarily assumed that the participant is a non-complier.

The CACE estimate will instead be obtained from the analysis LME model applying the strategies in table 7.7, as this adjusts for baseline and refers to the population for the supplementary investigation. The CACE estimate is the ratio of the estimated treatment effect to the proportion compliant, following the rule of thumb (31) (estimate LME/ proportion compliant).

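### The complier effect in SAP section 7.7.1 cannot shrink as the compliance cut-off rises from 50% to 95%, so the series cannot show whether higher compliance gives more benefit

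*SAP*

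**What the plan says.** Section 7.7.1 splits participants at a chosen percentage of sachets taken. It names the exclusion restriction, which it states as the assumption that "would-be non-compliers in the control group would have the same mean outcome as non-compliers in the intervention group". Because the number of sachets needed for an effect is not well studied, it says that "alternative levels of compliance will considered, ranging from 50% to 95" per cent; section 5.3.3 sets steps of 5%, which makes ten cut-offs.

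The estimator is then fixed: "The CACE estimate is the ratio of the estimated treatment effect to the proportion compliant". The treatment effect comes from the mixed model under the strategies of table 7.7, and missing compliance is primarily counted as non-compliance. The section calls the analysis more exploratory than the primary one. It also says that the approach should come closer to the true effect without the biases of a per-protocol analysis. Section 3.8 gives the purpose: to find out whether the effect may be much larger among compliers.

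**The concern.** A non-complier in this scheme is not someone who took nothing. It is anyone below the cut-off, and the cut-off moves. At 50% the assumption is that people who took less than half of their sachets got, on average, nothing from IPE over inulin. At 95% it covers everyone who took up to 94%. The higher the cut-off, the more participants with substantial intake are assigned no effect, and whatever benefit they had is credited to those above the line.

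At stake is the answer to the section 3.8 question. Ten estimates that grow with the cut-off invite the reading that better compliance brings more benefit. The arithmetic produces that pattern from any non-zero model estimate, provided that fewer participants reach each higher cut-off. The 95% figure could be reported as a several-fold larger effect in good compliers.

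**Working it through.** **Inputs from the SAP.** Section 4.5 plans for "90% power to detect a 2kg difference between arms in mean body weight change over 12 months". The test is two-sided at the 5% level, the SD is 4.35 kg, the allowance for dropout is 25%, and 202 participants with a 12-month outcome are needed. Allocation is 1:1 (section 4.2). The SAP states no CACE value and no expected compliance distribution.

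**The plan's own figure.** A t-based calculation with 2 kg, SD 4.35 kg, two-sided 5% and 90% power gives 100.4, so 101 per arm and 202 in total. 202/0.75 = 269.3, hence 270. The figures reproduce. They supply the standard error used in step 3.

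**Step 1: the table and the ratio are the same estimator.** Let p = N_I1/N_I be the proportion compliant in the IPE arm. The table gives M_I1 − [M_C − (1 − p)M_I2]/p. Since M_I = p·M_I1 + (1 − p)·M_I2, this equals (M_I − M_C)/p. Test values: M_I1 = 78, M_I2 = 80, M_C = 80.5, p = 0.6. The table gives 78 − (80.5 − 32)/0.6 = −2.83; the ratio gives (78.8 − 80.5)/0.6 = −2.83.

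**Step 2: direction.** CACE(t) = E/P(compliance ≥ t). E is one comparison of the randomised arms in the table 7.7 population and does not involve t. P(compliance ≥ t) cannot rise with t. So the absolute value of CACE(t) cannot fall between 50% and 95%, whatever the data.

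**Step 3: information.** Take E = −2 kg and SE = 4.35 × √(2/101) = 0.612 kg, and treat p as fixed.

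| p | CACE (kg) | SE (kg) | z |
|---|---|---|---|
| 0.8 | −2.5 | 0.77 | −3.27 |
| 0.5 | −4.0 | 1.22 | −3.27 |
| 0.2 | −10.0 | 3.06 | −3.27 |

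Estimate and SE scale together. The ten results are one result rescaled, and say nothing about whether more sachets give more benefit.

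**Step 4: size (assumed compliance and dose-response).**

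*Distribution A:* 25% of participants uniform on 0–50% compliance and 75% Beta(8, 1.5). Mean compliance is 0.25 × 0.25 + 0.75 × 8/9.5 = 0.694.
- Linear truth: effect proportional to intake, −2 kg at full intake. E = −2 × 0.694 = −1.39 kg.
- Threshold truth: −2 kg at 50% intake or more, none below. E = −2 × 0.743 = −1.49 kg.

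*Distribution B:* 20% uniform on 0–50% and 80% Beta(20, 1). Mean compliance is 0.812. With the linear truth, E = −2 × 0.812 = −1.62 kg.

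Each cell gives the SAP ratio / the true mean effect among those at or above the cut-off, in kg.

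| Cut-off | p in A | A, linear | A, 50% threshold | p in B | B, linear |
|---|---|---|---|---|---|
| 50% | 0.743 | −1.87 / −1.69 | −2.00 / −2.00 | 0.800 | −2.03 / −1.90 |
| 80% | 0.526 | −2.64 / −1.80 | −2.82 / −2.00 | 0.791 | −2.05 / −1.91 |
| 90% | 0.278 | −4.99 / −1.89 | −5.3 / −2.00 | 0.703 | −2.31 / −1.93 |
| 95% | 0.121 | −11.5 / −1.94 | −12.3 / −2.00 | 0.513 | −3.16 / −1.96 |

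Nobody in these scenarios can have an effect larger than −2 kg. The threshold column shows that the inflation does not need a linear dose-response: above 50%, extra sachets add nothing there, yet the ratio still grows about six-fold.

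**The case against.** The strongest defence is that the SAP discloses the assumption and has a reason for varying the cut-off. If IPE works only above some unknown intake, every cut-off at or below that intake is valid. This stands. Under distribution A with no effect below 80% intake, the ratio is unbiased from 50% to 80%. A reader might infer that the whole series is invalid; the document does not support that. The gap is that nothing warns of what happens above the intake at which IPE starts to act.

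Low cut-offs can also improve on the undivided model estimate. Under distribution A with a linear dose, the error at 50% is 0.18 kg against 0.30 kg for the undivided estimate, and at 70% it is 0.35 against 0.36. The ratio is worse from 75%.

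Third, the kilogram figures rest on assumed compliance. Distribution B gives −3.16 kg at 95% where A gives −11.5 kg. Only the direction is certain.

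Fourth, the analysis is supplementary. A reader might infer that a null trial could be turned into a positive one, or that the main result is inflated. Neither follows: z does not change across cut-offs with p treated as fixed, and the numerator is the table 7.7 estimate, not the primary estimate of section 7.2.

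Finally, dividing by mean intake also enlarges the estimate and has its own assumption. With the 80% threshold under distribution A it gives −1.05/0.694 = −1.52 kg, when the effect at full intake is −2 kg. That is a real limit of the alternative. However, it gives one figure and no series that looks like a gradient.

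**Conclusion.** The point holds for the supplementary analysis. By algebra and without assumptions, the estimate in section 7.7.1 cannot shrink as the cut-off rises, so the series cannot serve as evidence that higher compliance gives more benefit. The claim to come closer to the true effect cannot be made in general for cut-offs above the intake at which IPE starts to act. Calling the analysis exploratory and naming the exclusion restriction do not tell the reader that the restriction becomes harder to satisfy with each step.

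The size depends on compliance that the SAP does not give. In the three illustrations the ratio is 1.00 to 1.11 times the true effect at 50% (1.87/1.69 at most) and 1.6 to 6.1 times at 95% (3.16/1.96 to 12.3/2.00). If no intake below 95% had any effect, all ten estimates would be valid. The issue should be corrected before analysis, but the primary estimate, its test and its missing-data sensitivity analyses do not depend on it.

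**What to change.** Amend section 7.7.1 as follows, with matching edits in 5.3.3:

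1. Name 50% as the main CACE cut-off, and state that it relies on IPE having no average effect below 50% of sachets.
2. Add a randomisation-based instrumental-variable estimate with the proportion of sachets taken as a continuous exposure and randomised arm as the instrument. The simplest form is the table 7.7 model effect divided by the mean proportion taken in the IPE arm, read as the effect at full intake. State its linear-dose assumption. State also which value participants without compliance data receive, because section 7.6 only places them below 50%.
3. Drop the high cut-offs. If the series is kept, state beside it that it must rise with the cut-off by construction and is not evidence of dose-response.
4. Limit the claim about coming closer to the true effect to cut-offs at which the no-effect-below assumption is credible.

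The cost is SAP wording and one extra estimate from data already collected, with no extra participants. The downside is that the linear-dose assumption may not hold if the effect has a threshold, which is why the 50% CACE stays beside it.
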